Clinical trials identifier: **NCT03128658**

Principal Investigator: **[name]**

Protocol Title: **Trauma Induced Coagulopathy and Inflammation**

Date: **August 2, 2018**

Protocol Description: **This is a prospective observational trial designed to evaluate the factors that contribute to the development of trauma induced coagulopathy, post injury inflammation and the development of organ dysfunction in adult trauma patients. Demographic data, physiologic data, blood samples and clinical variables will be collected over the 5 days following traumatic injury.**

Protocol

Abstract

While a number of factors are known to be associated with the development of trauma induced coagulopathy (TIC), inflammation, and multi-organ failure, we currently cannot predict which patients are at risk for developing these life-threatening conditions with any certainty. In this prospective observational study, we will investigate the many factors that contribute to the development of trauma induced coagulopathy, post injury inflammation and the development of organ dysfunction in order to develop a multi scale computational algorithm and ex vivo models capable of clinical prediction. Using a convenience sample technique, demographic data, physiologic data, fresh and residual blood samples, urine samples, and clinical variables will be collected over 5 days following traumatic injury. In addition to a computational model, ex vivo models using microfluidic devices and high resolution cellular respirometry, and nucleic acid analysis will be used to predict the development of TIC and multi-organ failure.

Objectives

Overall objectives

1) Develop a computational algorithm to predict the development of trauma induced coagulopathy (TIC) 2) Validate ex-vivo microfluidic TIC models 3) Develop ex-vivo assays to predict the development of trauma-induced inflammation and the development of multi-organ failure

Primary outcome variable(s)

Coagulation parameters including thromboelastography and microfluidic assessment on admission, 3 hours, 6 hours, 12 hours, 24 hours, 48 hours, and 5 days post admission.

Secondary outcome variable(s)

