Patients who develop coagulopathy, altered cellular respiration, or multi-organ failure will be compared using T-tests or Mann-Whitney tests for continuous variables and Chi-squared or Fischers exact tests for dichotomous variables. Spearman's rank correlation will be used to assess associations between continuous variables. Logistic regression analysis will be used to identify risk factors for the development of trauma induced coagulopathy or multiorgan failure.. Receiver operating characteristic curves will be used to assess accuracy of microfluidic measurements compared to standard measures of coagulation . Continuous deidentified data including vital signs, laboratory values, and medications will be shared with collaborators at Princeton University in order to create a mathematical model. The computational whole-patient systems model is a multiscale, multi-compartment model whose state-space is defined by a very large and heterogeneous set of variables as well as a large number of input parameters. It is straightforward to make direct contact with the clinical trauma blood profiles because the measured variables in these profiles are also included in the model state space. This comparison first will be used to establish the validity of the model. Here, the model will simply be integrated in time for various initial trauma conditions in an attempt to determine whether the model can be predictive. In particular, we will determine whether it is possible to reproduce the variation between the various time states at admission,3, 6, 12, 24, 48 hours and 5 days post admission. A more challenging data mining application is to discover new variables that are more predictive of clinical outcomes than those employed in current clinical protocols. The workhorse data mining technique we plan to explore, extend, and use to establish links between our multiscale model and clinical data is known as Diffusion Maps. This is a framework based upon diffusion processes for finding meaningful geometric descriptions of data sets, even when the underlying geometry of the data is complex, nonlinear and corrupted by noise. The method is based on the construction of a Markov transition probability matrix corresponding to a random walk on a graph whose vertices are the data points with transition probabilities being the local similarities between pairs of data points. The framework relates the spectral properties of Markov processes to their geometric counterparts and it unifies ideas arising in a variety of contexts such as nonlinear dimensionality reduction methods, machine learning, and harmonic analysis. The first few eigenvectors of the sparse Markov matrix are then used to generate a new set of intelligent coordinates that embody the intrinsic geometry of the data set. These are the diffusion map coordinates. Most importantly, these eigenvectors integrate the local similarities into a globally efficient low-dimensional representation of the complex geometric structure. The usage of eigenvectors of similarity matrices for dimensionality reduction is not new. In fact, the classical method of principal component analysis (PCA) computes principal components as eigenvectors of the covariance matrix of the data set and find a low dimensional representation of the data by projecting it onto the subspace spanned by the first few principal components that capture the most variability (or energy) of the data. Diffusion Maps is a successful generalization of PCA to complex nonlinear data sets whose structure is unknown in advance: unlike PCA, the diffusion map coordinates are nonlinear projections of the data; moreover, the nonlinear embedding is based only upon local similarities of neighboring data points. Diffusion Maps first will be used on the multiscale simulation data sets. This will establish macroscopic observables that define the trajectory of the overall patient-scale model. This is crucial because it is much simpler to establish a connection to patient outcome when only a few variables are being tracked (instead of the large variable space that defines the full multiscale model). However, these variables are generally not obviously connected to clinical variables and we will use the simulation data to establish relationships between the Diffusion Maps variables and actual measureable quantities. The result of this work will be to isolate variables that are highly predictive of patient outcome and allow assessment of different interventions.

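### The computational model is judged valid by whether it can reproduce the time course, a test with no failure criterion, and no stated analysis scores the model on TIC prediction

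*Combined protocol and SAP*

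**What the plan says.** Under Objectives, the first of three overall objectives is a computational algorithm that predicts TIC. The second is to validate the microfluidic models.

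The Analysis Plan describes the whole-patient model as one whose "state-space is defined by a very large and heterogeneous set of variables as well as a large number of input parameters". De-identified vital signs, laboratory values and medications from study patients "will be shared with collaborators at Princeton University in order to create a mathematical model".

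On comparing the model with the clinical blood profiles, the plan says: "This comparison first will be used to establish the validity of the model". The method is that "the model will simply be integrated in time for various initial trauma conditions in an attempt to determine whether the model can be predictive". The one concrete question follows: "we will determine whether it is possible to reproduce the variation between the various time states", covering admission, 3, 6, 12, 24 and 48 hours, and 5 days.

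The only accuracy measure in the section belongs elsewhere: "Receiver operating characteristic curves will be used to assess accuracy of microfluidic measurements" against standard coagulation measures. TIC enters the group comparisons and a logistic regression for risk factors. A later Diffusion Maps stage looks for variables that predict clinical outcome better than those in current use, and gives no metric.

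**The concern.** Reproducing how values change over time is a different task from predicting which patient becomes coagulopathic. The plan uses the first as its test of validity and never states a test of the second.

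Three things are left open: what result would count as failure, whether parameters are fixed before the comparison, and whether the patients used for comparison differ from those used for building. With all three open, a favourable result on the time course would not show that the first objective has been achieved. The Accrual section justifies the large enrolment by the need for a model that accurately identifies predictors of TIC, inflammation and multiorgan failure, so the missing test concerns a main reason for the size of the study.

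**Working it through.** **No figure to reproduce.** The documents give 300 subjects. They give no target AUC, acceptance limit, power calculation or parameter count.

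**Step 1: does any stated analysis score the computational model on TIC?** Taking the methods of the Analysis Plan in turn:

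- Group tests (t, Mann-Whitney, chi-squared, Fisher): TIC is a grouping variable; no prediction is scored.
- Spearman correlation: association between continuous variables only.
- Logistic regression: risk factors for TIC or multiorgan failure; no discrimination, calibration or validation is stated, and it is not the computational model.
- ROC curves: microfluidic measurements only.
- Forward integration: reproduction of the time course; no measure or limit.
- Diffusion Maps: applied first to simulated data, then linked to measurable quantities and patient outcome; no metric.

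None does. Data and Safety Monitoring adds an analysis after every 50th subject (300/50 = 6 looks if all enrol) but reserves no patients for validation. No section gives an operational definition of TIC or a time window for it.

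**Step 2: why parameter locking matters.** This is a conditional illustration, not a statement about this model. Suppose k free linear parameters, including the level, are tuned to one trajectory of T points that is pure noise. The expected in-sample R² is (k − 1)/(T − 1). With T = 7 time states:

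- k = 3: 2/6 = 0.33
- k = 5: 4/6 = 0.67
- k = 7: 6/6 = 1.00

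Simulation with 4,000 noise trajectories per k gave 0.33, 0.67 and 1.00. The Accrual section allows some variables to be missing at some time points. T can then be below 7, and the same k fits more closely. The values of k are assumptions. If all parameters were locked beforehand, this calculation would not apply.

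**Step 3: what a TIC score could deliver.** Assume 25% TIC; the Background says about a quarter of trauma patients, which is not a design input. The Hanley-McNeil variance of an AUC A, with n1 cases and n0 non-cases, is

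[A(1 − A) + (n1 − 1)(q1 − A²) + (n0 − 1)(q2 − A²)] / (n1·n0), where q1 = A/(2 − A) and q2 = 2A²/(1 + A).

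For A = 0.80: q1 = 0.6667, q2 = 0.7111, A² = 0.64.

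- All 300 scored (75 cases, 225 non-cases): (0.16 + 74×0.02667 + 224×0.07111)/16,875 = 18.06/16,875 = 0.001070; SE 0.0327; half-width 1.96×0.0327 = 0.064.
- 100 held out (25 cases, 75 non-cases): (0.16 + 24×0.02667 + 74×0.07111)/1,875 = 6.06/1,875 = 0.003233; SE 0.0569; half-width 0.111.

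At AUC 0.70 / 0.90 the half-widths are 0.073 / 0.048 with 300 scored and 0.126 / 0.084 with 100. With 50 held out (about 12 cases) the half-width is 0.161 at AUC 0.80.

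These are for a single AUC. The interval for a difference between two scores in the same patients also depends on how strongly the scores are correlated, which is unknown. Excluding TIC already present at admission would lower the case count below the one assumed here and widen the intervals.

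**The case against.** The plan describes forward simulation from starting conditions, not a search for a parameter setting that fits, and a forward run can fail. Its wording, an attempt to determine whether the model can be predictive, allows a negative answer. This stands. A reader might infer that the test can hardly be failed, but the documents do not establish that: they are silent on whether parameters are locked or tuned.

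A reader might also infer that between-time variation is only an average pattern, so that a curve of time means would pass. The text does not say so. It speaks of various initial conditions and of blood profiles, and on that reading one common curve would not suffice. Nor can one infer that the model would do worse than a patient's own admission value. Any figure for that comparison would rest on an assumed correlation between time points and an assumed TIC definition, neither of which is in the documents.

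It can further be said that the comparison is described as a first step, that the Diffusion Maps stage names currently used variables as a comparator, that the time states probably include coagulation values, and that the first objective says develop while only the second says validate. These points limit the claim. They do not remove it, because the plan itself says the comparison is to establish the model's validity, and none of these elements supplies a performance measure for the model's TIC prediction.

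**Conclusion.** The concern holds in a limited form. The stated validity test has no failure criterion, no locking of parameters and no separation of building from testing patients. A model with many tunable parameters could pass it without predicting who develops TIC, and no stated analysis scores the computational model on TIC. This rests on reading the text and needs no numerical assumption.

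How far a favourable result could mislead cannot be quantified, since parameter handling, parameter count and TIC definition are not given. The R² values show only what unrestricted tuning would permit. It also does not follow that the first objective will be reported as met without a test; the point is that the plan sets none. The change is worth making before the model is compared with patient data, but the group comparisons, the logistic regression and the microfluidic ROC analysis do not depend on it.

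**What to change.** In the Analysis Plan:

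1. State an operational TIC definition and time window, chosen by the investigators from the coagulation measures already collected. Count only TIC arising after admission as predicted TIC.
2. Lock all model parameters before the comparison. Start the model from each patient's admission data, and state whether recorded treatments are used as inputs.
3. Score only patients not used to build or tune the model, by a held-out set or cross-validation.
4. Report patient-level forecast error at the later time points against two benchmarks: the mean at each time, and a regression on the patient's admission value.
5. Report AUC and calibration for TIC against a logistic model of standard admission variables.
6. Fit and score the benchmarks under the same out-of-sample scheme, and give 95% confidence intervals for the differences.
7. Describe the model as predictive of TIC on the basis of these results, not on reproduction of the time course alone.

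Cost: analysis-plan wording and a little more analysis, with no new samples. Deferred or missing samples, deaths and early discharges will reduce the number of patients scored, so the rule for handling them should be written down at the same time. Intervals will be wide (about ±0.06 to ±0.11 at AUC 0.80 under the assumptions above), and the resulting claim may be less favourable.

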Respirometry of platelets, peripheral blood mononuclear cells, and neutrophils on admission, 3 hours, 6 hours, 12 hours, 24 hours, 48 hours, and 5 days post admission; Development of multiorgan failure within 30 days of admission; Level of free serum free nucleic acids; Expression of pro and anti-inflammatory proteins and genes and genetic variants in serum, platelets, and white blood cells.

Background

Traumatic injury results in 5-6 million deaths per year worldwide with \$518 billion global cost with about half of trauma deaths due to acute blood loss. Acute blood loss and standard resuscitation with crystalloids and stored blood products causes hypothermia, acidosis, tissue hypoxia, hypotension, inflammation, the activation and consumption of coagulation factors including platelets, the release of free nucleic acids, the development of mitochondrial dysfunction and eventually organ failure. Importantly, about a quarter of trauma patients display a coagulopathy, (trauma induced coagulopathy, TIC) which greatly increases the risk of death and/or the development of multiorgan failure. We currently, however, cannot predict who will develop TIC or its associated complications. In fact, two patients who have the same clinical presentation may have very different outcomes. Developing a multi scale computational model and ex-vivo point of care assays would allow us to efficiently identify and effectively treat at risk patients and potentially improve outcomes.

Study Design

Phase*

Not applicable

Design

Prospective, observational, convenience sampling of trauma patients 18 yrs old or older who present to the trauma bay will be included. Minimally injured patients will be compared to those with a systolic blood pressure of 90 mmHg or less, the need for blood product transfusion within 1 hour of admission, and/or an ISS of greater than or equal to 15. Demographic data including past medical/medication history as well as clinical data including continuous vital signs (when available) will be recorded. Blood samples (approximately 15 ml) and urine samples (approximately 10 ml) will be taken on admission, 3hr, 6hrs, 12hrs, 24 hrs, 48 hrs, and 5 days post admission. Residual blood samples (which would otherwise be discarded) will be obtained from the PPMC clinical laboratory on 0 and 2 days post admission. Blood samples may be analyzed for coagulation parameters included ex vivo microfluidic

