48 hours and 5 days post admission. Blood and urine sample collection in unstable patients will be deferred or delayed if it is determined by the clinical team that taking the sample would interfere with clinical care. Smaller blood and urine volume samples maybe taken at each time point (eg 10 ml rather than 15 ml of blood) if research expertise is not available for sample analysis (e.g microfluidic or high resolution respirometry) at that time point. Residual plasma and whole blood samples will be collected from the PPMC clinical laboratory on day 0 and day 2 from trauma bay admission. Blood samples will be analyzed for coagulation and microfluidic flow parameters, proteins involved in inflammation and coagulation, mitochondrial function and respiration of white blood cells and platelets, DNA sequencing of specific genes involved in organ failure, and gene expression of proteins of interest. Residual samples will be further studied for protein biomarker measurements and DNA analyses. Urine samples will be analyzed for biomarkers of organ injury and dysfunction. Vital signs, number of blood transfusions, volume of crystalloid, administration of medications, and the values of routine laboratories will be monitored continuously for 24 hours, and then cumulatively for up to 5 days. This data will be collected by reviewing the electronic medical record via EPIC. Discrete data will be recorded on case report forms and then entered into REDCap - an institutionally approved and managed secure network that is also password protected. Continuous data will be deidentified and maintained on REDCap. The development of multiorgan failure will be monitored for up to 30 days post enrollment. If patients are discharged or die prior to completing the 5 days of blood samples, additional samples and/or clinic appointments for the purpose of research will not be obtained. After the last blood draw, we will be following the patient's outcome until discharge. This data is routinely extracted as part of the Pennsylvania Trauma Outcomes Study - a state trauma center requirement - and will not require additional contact with the patient. We will not personally follow up patients if they are discharged prior to 30 days.

The following documents are currently attached to this item:

There are no documents attached for this item.

Deception

Does your project use deception?

No

Analysis Plan

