Biometric identifiers, incl. finger and voice prints
Full face photographic images and any comparable images
Any other unique identifying number, characteristic, or code

None

Does your research request both a waiver of HIPAA authorization for collection of patient information and involve providing Protected Health Information ("PHI") that is classified as a "limited data set" (city/town/state/zip code, dates except year, ages less than 90 or aggregate report for over 90) to a recipient outside of the University of Pennsylvania covered entity?

No

Tissue Specimens Obtained as Part of Research*

Are Tissue Specimens being obtained for research?
 Yes

Tissue Specimens - Collected during regular care*

Will tissue specimens be collected during regulator clinical care (for treatment or diagnosis)?
 Yes

Tissue Specimens - otherwise discarded*

Would specimens otherwise be discarded?

No

Tissue Specimens - publicly available*

Will tissue specimens be publicly available?

No

Tissue Specimens - Collected as part of research protocol*

Will tissue specimens be collected as part of the research protocol?

Yes

Tissue Specimens - Banking of blood, tissue etc. for future use*

Does research involve banking of blood, tissue, etc. for future use?

Yes

Genetic testing

If genetic testing is involved, describe the nature of the tests, including if the testing is predictive or exploratory in nature. If predictive, please describe plan for disclosing results to subjects and provision of genetic counseling. Describe how subject confidentiality will be protected Note: If no genetic testing is to be obtained, write: "Not applicable."

The concentration of free nucleic acids in the serum will be measured. We will measure the expression of pro- and anti-inflammatory genes by extracting RNA from white blood cell populations and platelets and creating a cDNA library for the gene expression of proteins of interest that will be studied. Further, the DNA sequences of these proteins will be analyzed to look for polymorphisms associated with organ failure. The results of these investigations will only be linked to the patient's study number and not their name.

Consent

1. Consent Process

Overview

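### Free nucleic acids are to be measured in serum, which requires the blood to clot, so the level may vary with the clotting defect under study

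*Combined protocol and SAP*

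**What the plan says.** Serum is named for free nucleic acids in two places. Under Secondary outcome variable(s) the item reads "Level of free serum free nucleic acids", and Genetic testing states "The concentration of free nucleic acids in the serum will be measured". No other matrix is named for this analyte.

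For inflammatory markers the secondary outcomes give one pooled item: "Expression of pro and anti-inflammatory proteins and genes and genetic variants in serum, platelets, and white blood cells". Procedures names no matrix for the inflammatory proteins measured in the fresh samples.

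Plasma appears as a specimen only in Procedures: "Residual plasma and whole blood samples will be collected from the PPMC clinical laboratory on day 0 and day 2 from trauma bay admission". Those residual samples go to protein biomarkers and DNA analyses; free nucleic acids are not listed for them.

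The Abstract lists nucleic acid analysis among the methods for predicting TIC and multi-organ failure. The Analysis Plan says "Patients who develop coagulopathy, altered cellular respiration, or multi-organ failure will be compared using T-tests or Mann-Whitney tests for continuous variables" and "Logistic regression analysis will be used to identify risk factors for the development of trauma induced coagulopathy or multiorgan failure". The document gives no tube type, anticoagulant, clotting time, time to separation, or rule for samples that clot slowly or incompletely.

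**The concern.** A serum level is the circulating level plus whatever cells and platelets release in the tube. In most studies that extra part is a nuisance of roughly equal size in every group. Here the groups are defined by how well their blood clots, and Background itself describes clotting factors and platelets being activated and consumed after injury. The extra part can therefore differ between the groups, which makes the error potentially differential with respect to the outcome. A larger sample does not average that out.

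At stake is how the free nucleic acid result can be read. A marker that partly records in-tube clotting would be partly circular as a predictor of TIC. It could also carry TIC status into the model for multiorgan failure. Once a tube has clotted, the circulating level cannot be recovered from it.

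**Working it through.** The documents give no figure on this point, so there is none to reproduce. The two calculations below show how much an artefact of this kind could matter. They do not estimate how large it is.

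**1. Ratio of serum levels, TIC to non-TIC**

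Inputs, all assumed:
- c: true ratio of circulating levels, 1 or 1.5.
- k: in-tube release as a multiple of the circulating level in normally clotting blood, 1 or 5.
- r: proportional reduction of release in TIC blood, 0.2 or 0.5. Negative r means more release in TIC.

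Observed ratio = (c + k(1 − r)) / (1 + k). This is a weighted average of the true ratio c and the release ratio 1 − r, with weights 1/(1 + k) and k/(1 + k).

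| Release in TIC | k | c = 1 | c = 1.5 |
|---|---|---|---|
| 20% lower | 1 | 1.8/2 = 0.90 | 2.3/2 = 1.15 |
| 50% lower | 1 | 1.5/2 = 0.75 | 2.0/2 = 1.00 |
| 20% lower | 5 | 5.0/6 = 0.83 | 5.5/6 = 0.92 |
| 50% lower | 5 | 3.5/6 = 0.58 | 4.0/6 = 0.67 |
| equal | 1 | 2.0/2 = 1.00 | 2.5/2 = 1.25 |
| equal | 5 | 6.0/6 = 1.00 | 6.5/6 = 1.08 |
| 20% higher | 1 | 2.2/2 = 1.10 | 2.7/2 = 1.35 |
| 50% higher | 1 | 2.5/2 = 1.25 | 3.0/2 = 1.50 |
| 20% higher | 5 | 7.0/6 = 1.17 | 7.5/6 = 1.25 |
| 50% higher | 5 | 8.5/6 = 1.42 | 9.0/6 = 1.50 |

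Equal release only dilutes a real difference. Unequal release can create a difference where there is none, in either direction. A true 1.5-fold rise is reversed (ratio below 1) only when k × r exceeds c − 1 = 0.5. That occurs in the k = 5 rows with lower release (k × r = 1.0 and 2.5) and never at k = 1 (0.2 and 0.5).

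**2. False findings from a small artefact**

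Inputs: 300 subjects (planned enrolment) and about a quarter with coagulopathy (Background), giving 75 against 225. Assumed: complete data, no true difference, a two-sided 5% test, and a shift of s standard deviations (SD) due only to specimen preparation.

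Standard error = √(1/225 + 1/75) = 0.133 SD. Chance of a significant result = Φ(s/0.133 − 1.96) + Φ(−s/0.133 − 1.96). Spurious area under the ROC curve = Φ(s/√2).

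| Shift (SD) | Chance of a false finding | Spurious area |
|---|---|---|
| 0 | 5.0% | 0.50 |
| 0.1 | 11.7% | 0.53 |
| 0.2 | 32.3% | 0.56 |
| 0.3 | 61.4% | 0.58 |
| 0.5 | 96.3% | 0.64 |

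For s = 0.2: 0.2/0.133 = 1.5, Φ(−0.46) = 0.323, and the other tail is negligible.

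**The case against.** The strongest reply is that serum may be loose wording. The text is an ethics application, not a laboratory manual. The Genetic testing sentence answers a prompt about the nature of tests and confidentiality, and the wording of the secondary outcome is visibly garbled. This may be right. But serum is named in both places and no other matrix is given, so if plasma was meant, both places still need correcting.

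Several stronger readings are tempting, and the documents do not support them.
- *The bias is known to mask or reverse a rise in TIC.* The documents give neither its size nor its direction. Ratios of 0.58 to 1.15 follow only if release is lower in TIC. If slower clotting lengthened contact with the cells and raised release, equal circulating levels would look like a rise.
- *The inflammatory proteins are affected in the same way.* The only support is one pooled item that lists proteins, genes and variants against three matrices. Residual plasma or whole blood already supplies protein biomarkers on days 0 and 2.
- *Plasma is already available for this analyte.* The plasma named is clinical-laboratory residual on two days only. The document does not say how the fresh 15 ml is divided, and the draw can fall to 10 ml. What can be said is that respirometry of platelets and white cells, listed for all seven time points, needs unclotted blood, so handling it is already part of the work.
- *The main results are compromised.* This is a secondary outcome. The Analysis Plan does not name free nucleic acids, and the data it lists for the computational model are vital signs, laboratory values and medications.

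The reply about cost also has weight. With an anticipated start in February 2017 and this version dated August 2018, serum may already be stored for a good part of the cohort.

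**Conclusion.** The point holds for free nucleic acids. As written, the plan measures this secondary outcome in a specimen whose preparation depends on the process that defines the comparison groups, and no processing or analysis step controls for that. The result is an uncontrolled and potentially differential measurement error of unknown size and direction.

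The ratios rest on assumed release of 1 to 5 times the circulating level and an assumed 20-50% difference by TIC status. Without a true difference they run from 0.58 to 0.90 if release is lower in TIC, and from 1.10 to 1.42 if it is higher. The false-finding rates rest on an assumed 75 against 225 split with complete data; under that split an artefact of 0.2 SD would give a false finding in about one comparison in three.

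For soluble inflammatory proteins the point is conditional: it applies only where serum is in fact the intended matrix for the fresh samples. The change should be made, but it does not bear on the primary coagulation outcomes.

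**What to change.** - Under Secondary outcome variable(s) and in Genetic testing, replace serum with anticoagulated, cell-free plasma for free nucleic acids. Take it from the existing 15 ml draw and state a fixed time from draw to separation. The choice of anticoagulant and centrifugation steps can be left to the laboratory, provided it is written down and kept constant.
- State the matrix for soluble inflammatory proteins in the fresh samples. Wherever serum is the intended matrix, make the same change.
- If serum has been stored for earlier subjects, do not pool its values with plasma values. Analyse it separately or include specimen type as a stratum. Stratifying prevents mixing of the two scales but does not remove the error within the serum stratum, so the plasma results should carry the inference.

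The cost is a change of tube and processing wording within the same blood volume, and a split series for this secondary outcome, with fewer subjects in each part.
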